8.5.1. Adverse Events

The AEs reporting period for safety surveillance begins when the subject signs the ICF and ends at his/her last FU visit. Investigators are not obliged to actively seek SAEs after the CSP-defined FU period. However, if the investigator is informed about an SAE that occurs at any time after

the subject's post-treatment FU visit and the event is deemed related to the use of IP, they should promptly document and report the event to the sponsor by using the SAE form.

Detailed definitions, reporting period, ratings and reporting requirements for AEs and SAEs are found in Section 11.

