- **QuantiFERON-TB Gold test** to check for latent or active TB (at screening). TB results should be reported by the investigator as required by local law.
- **SARS-CoV-2:**
IgM Immunoassay.
RT-PCR from a nasal swab sample to check for SARS-CoV-2 infection at screening and RT-PCR from a nasal swab sample and serology testing at baseline, and throughout the study as needed (when SARS-CoV-2 symptoms present). The repeat RT-PCR may be performed 2-3 days prior to the baseline visit to allow for results availability prior to randomization. Positive SARS-CoV-2 results should be reported by the investigator as required by local law.

The clinical laboratory evaluations will be performed at visits specified in the Schedule of Activities in Section 8.11 (see also Section 8.1, “[Timing of Assessments](#)”). Reference ranges will be supplied by the central laboratory. Clinical laboratory values outside the normal range will be flagged and clinical relevance will be assessed by the investigator. Only laboratory test abnormalities judged as clinically significant by the principal investigator should be recorded as AEs. At the discretion of the investigator, when following up AEs, additional laboratory parameters may be tested, and additional samples taken.

Blood and urine sample handling and shipment instructions will be provided in a separate laboratory manual.

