11. SAFETY REPORTING

11.1. Definitions of Adverse Events, Serious Adverse Events, and Special Situations

11.1.1. Adverse Events

An AE is any untoward medical occurrence, new or worsening of any pre-existing condition, in a clinical study subject administered a medicinal product and which does not necessarily have to have a causal relationship with this treatment.

An AE can therefore be any unfavorable and unintended sign (e.g. an abnormal laboratory finding), symptom, or disease temporally associated with the use of a medicinal product, whether or not considered related. AEs may also include pre- or post-treatment complications that occur as a result of CSP-specified procedures, worsening of the targeted disease, overdose, drug abuse/misuse reports, or occupational exposure. Pre-existing conditions that increase in severity or change in nature during or as a consequence of participation in the clinical study will also be considered AEs.

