11.1.4. Adverse Events of Special Interest

Not applicable.

11.1.5. Clinical Laboratory Abnormalities and Other Abnormal Assessments as Adverse Events or Serious Adverse Events

Laboratory abnormalities without clinical significance based on the investigator's judgment are not considered AEs or SAEs. However, laboratory abnormalities (e.g. clinical chemistry, hematology, and urinalysis) or other abnormal (clinical study-specific) assessments (e.g. ECG, radiography, vital signs) that require medical or surgical intervention, are associated with signs and/or symptoms, and/or lead to IP interruption, modification or discontinuation must be recorded as an AE or SAE if they meet the definition as described in Sections 11.1.1 and 11.1.2, respectively. If the laboratory abnormality is part of a syndrome, the syndrome or diagnosis is to be reported (e.g. anemia instead of decreased hemoglobin).

The following liver enzyme elevations must be reported as SAEs:

- AST or ALT $\geq 3 \times \text{ULN}$ with signs of liver damage (total bilirubin $> 2 \times \text{ULN}$ OR INR > 1.5 , and/or with the appearance of fatigue, nausea, vomiting, right upper quadrant pain or tenderness, fever, rash and/or eosinophilia [$> 5\%$]).

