Appendix 15: Algorithm for Elevated Liver Function Tests

	AST or ALT increase to				
Value Range	>=1.5x to 3xULN	>=3x to <5xULN	>=5x to <8xULN	>=3xULN with signs of liver damage ¹	>=8xULN
IP Action	Continue as planned	Reduce or interrupt IP for at least 2 weeks	Interrupt IP for at least 2 weeks	Discontinue IP ²	Discontinue IP ²
		Close observation ²	Close observation ²		
After at least 2 weeks	AST and ALT <3xULN	AST or ALT >=3xULN			
	Weekly LFTs for the first 2 weeks (biweekly for the following weeks, or more frequently at investigator's discretion)	Discontinue IP Report SAE and complete liver event page for any of abnormalities listed below ³ : - AST/ALT increase >=3xULN with signs of liver damage ¹			

¹ Signs of liver damage:

- total bilirubin >=2.0xULN OR INR >1.5, and/or
- symptoms: appearance of fatigue, nausea, vomiting, right upper abdominal quadrant pain or tenderness, fever, rash and/or eosinophilia (>5%)

² Close observation recommendations:

- Monitor 2 to 3 times per week all of the following parameters: ALT, AST, alkaline phosphatase, total bilirubin, eosinophils, INR. If local regulations allow, home visits can be performed if subjects cannot come to the clinical study center.
- Frequency of retesting can be reduced to once a week or less if abnormalities stabilize or the IP has been discontinued; however, monitoring might still be needed more frequently taking into consideration the SoC and/or changes to this.
- Based upon investigator's discretion gastroenterology or hepatology consultations, additional serology testing, imaging, and pathology assessments may be required.
- Re-query history of symptoms, prior and concurrent diseases, concomitant medication and non-prescription medicines, herbal, dietary supplements, alcohol use, recreational drug use, special diets.

- Rule out all of the following: acute viral hepatitis, autoimmune hepatitis, alcoholic hepatitis, non-alcoholic fatty hepatitis, hypoxic/ischemic hepatitis, biliary tract disease, and cholestasis.

- Re-query exposure to environmental chemical agents.

³ The following steps should be followed:

- The site should immediately contact the subject and require the subject to discontinue IP immediately. The subject should be asked to return to the site within a 48-hour window from awareness of the result.
- A full evaluation of various causes of hepatitis should be conducted (i.e. infectious, alcohol, medications, anatomical).

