#### **6.3.1.8. Presentation of Results**

The analysis will focus on AEs reported during the treatment period. AEs reported during the screening period will only be listed.

All AEs tables will show the number of subjects with TEAEs.

AEs which are not treatment-emergent will only be listed.

A summary table will be provided, showing the number (percent) of subjects with at least one:

- TEAE,
- IP-related TEAE,
- Serious TEAE,
- TEAE leading to death,
- TEAEs by worst intensity (CTCAE Toxicity Grade),
- TEAE leading to IP interruption,
- TEAE leading to IP discontinuation.

The AE terms will be presented sorted in descending order of frequency, prioritizing the GLPG3970 treatment group and then for placebo, first by system organ class, then by preferred term, and then alphabetically.

Frequency tabulations, by system organ class and preferred term, of the number (percent) of subjects with a TEAE will be presented. Similar tables will be provided by worst intensity, and for IP-related TEAEs, grade 3-4-5 TEAEs, serious TEAEs and TEAEs leading to IP discontinuation of IP.

All AE data will also be listed, including separate lists for SAEs, AEs leading to death, and AEs leading to IP discontinuation. Listings will clearly indicate AEs to be treatment-emergent or not.

In addition, AEs related to SARS-CoV-2 will be listed separately.

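### Protocol 8.5.2 and 11.1.5 give different AE-recording rules for AST/ALT rises that stop dosing without signs of liver damage

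*Protocol*

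**What the plan says.** Protocol 8.5.2 closes its list of laboratory tests with one recording rule: "Only laboratory test abnormalities judged as clinically significant by the principal investigator should be recorded as AEs". The sentence carries no exception and no reference to Section 11.

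Protocol 11.1.5 begins from the same position: "Laboratory abnormalities without clinical significance based on the investigator's judgment are not considered AEs or SAEs". It then makes an exception. Abnormalities that need medical or surgical intervention, come with signs or symptoms, "and/or lead to IP interruption, modification or discontinuation must be recorded as an AE or SAE if they meet the definition" in 11.1.1 or 11.1.2. On that definition, 11.1.1 says "An AE can therefore be any unfavorable and unintended sign (e.g. an abnormal laboratory finding), symptom, or disease temporally associated with the use", meaning use of a medicinal product; it does not make clinical significance a condition.

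Section 8.5.1, immediately before 8.5.2, tells the reader where the full rules are: "Detailed definitions, reporting period, ratings and reporting requirements for AEs and SAEs are found in Section 11".

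The dosing rules for liver enzymes in 6.4 and Appendix 15 work on multiples of ULN. For AST or ALT from 5 to below 8 x ULN, Appendix 15 tells the site to "interrupt IP for at least 2 weeks". At 8 x ULN or above, both places call for discontinuation.

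SAP 6.3.1.8 summarizes subjects with at least one "TEAE leading to IP interruption" and, separately, with a TEAE leading to IP discontinuation.

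**The concern.** Under 8.5.2 read by itself, an enzyme rise that crosses a numeric threshold and stops dosing is not an AE unless the investigator also calls it clinically significant. Under 11.1.5 the dosing action is itself a reason to record it. The dosing trigger is a number and the 8.5.2 recording trigger is a judgment, so the two can part company.

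The number, incidence and severity of TEAEs is a primary endpoint (Protocol 4.1). SAP section 1 reports that the study was terminated after a liver toxicity signal and that only the primary endpoint and safety analyses remain. A TEAE must first exist as an AE record (Protocol 9.3.5.2, SAP 6.3.1.1), and the action taken with IP is an attribute of that record (Protocol 11.2.1). With no AE record there is nothing for the TEAE rows to count.

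**Working it through.** The plan gives no figure to reproduce; the check is a comparison of passages.

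**Step 1. Is the conflict one of wording?** The parallel sentences for physical examination (8.5.3), vital signs (8.5.4) and ECG (8.5.5) say that clinically significant findings should be recorded as AEs. They do not say that nothing else should be, so they are compatible with 11.1.5. Only the laboratory sentence is exclusive.

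**Step 2. Does the condition in 11.1.5 remove the conflict?** Recording there depends on the finding meeting the definition. Since 11.1.1 names an abnormal laboratory finding as an example, an enzyme rise after dosing can meet it whatever the significance judgment. The condition makes the duty less than absolute but does not restore the 8.5.2 rule.

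**Step 3. Which liver findings are affected?**

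| AST/ALT finding | IP action | 8.5.2 | 11.1.5 |
|---|---|---|---|
| 3 to <5 x ULN, no signs | Reduction or interruption (to be considered in 6.4; the listed action in Appendix 15) | AE only if judged significant | Recorded if dosing is changed and the definition is met |
| 5 to <8 x ULN, no signs | Interruption | AE only if judged significant | Recorded if the definition is met |
| Still >=3 x ULN after at least 2 weeks, no signs | Discontinuation (Appendix 15) | AE only if judged significant | Recorded if the definition is met |
| >=8 x ULN, no signs | Discontinuation | AE only if judged significant, unless the 6.4 SAE sentence applies | Recorded if the definition is met; not on the mandatory SAE list |
| >=3 x ULN with signs of liver damage | Discontinuation | Not decisive | Mandatory SAE, as also in 6.4 and Appendix 15 |

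The last row is outside the problem. In the fourth row, the 6.4 sentence requiring SAE reporting stands at the end of the with-signs bullet, and the text does not settle whether it also covers the bullet for >=8 x ULN.

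**Step 4. What would one unrecorded case change?** The planned arms are 20 on GLPG3970 and 10 on placebo (Protocol 9.1).

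- GLPG3970: 1/20 = 5 percentage points.
- Placebo: 1/10 = 10 percentage points.

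These are the shifts in an interruption or discontinuation row when the subject has no other TEAE counted there. The any-TEAE incidence moves only if the subject has no other TEAE at all; the count of events falls by one in either case. The study stopped early, so the actual denominators are unknown.

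**Step 5. Where would the case still be seen?**

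- SAP 6.3.2.8 and 6.3.2.9 tabulate AST/ALT multiples and toxicity grades from central laboratory values, without reference to AE records.
- SAP 6.1.3 tabulates reasons for discontinuing IP by arm.
- SAP 6.1.8.2 lists deviations from the dosing schedule.

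These do not fully replace the AE rows. No tabulation of reasons for interruption is specified, the laboratory tables do not link a value to a dosing action, and local laboratory results are only listed (SAP 6.3.2.1).

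**The case against.** The strongest reply is that these are not two equal rules. Section 8.5.1 sends the reader to Section 11, and 11.1.5 opens with the 8.5.2 principle before stating exceptions. The natural reading is a short general statement in the assessment section and the governing rule in the reporting section. This stands in large part: it shows which rule was probably intended. It does not correct an exclusive sentence in the section a site consults when reviewing laboratory results.

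Second, the loss needs an unusual judgment. An investigator would have to call a value that stopped dosing not clinically significant, although laboratory alerts go to the investigator and sponsor at Grade 3 and above (Protocol 5.5) and SAP Table 7 places AST/ALT above 5 x ULN at H3. This also stands, and it makes the event unlikely but not impossible.

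Third, reconciling AE and dosing records is normally covered in data management or medical review plans, which Protocol 12.7.1 mentions but which are not part of these documents. Their content is unknown, so one cannot say that the check is missing.

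A reader might infer that any protocol-driven liver stop could escape the TEAE tables. The documents do not support that, because stops with signs of liver damage are mandatory SAEs.

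**Conclusion.** The inconsistency is real and narrow. It concerns AST/ALT rises without signs of liver damage that trigger the numeric dosing rules and that the investigator judges not clinically significant. For these, 8.5.2 and 11.1.5 give different answers on AE recording. The exposed outputs are the TEAE counts and the SAP 6.3.1.8 rows on interruption and discontinuation, by up to 5 points per GLPG3970 subject or 10 points per placebo subject at the planned sizes. Visibility elsewhere assumes that the disposition and dosing outputs are among those kept after the early stop.

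A reader might go further and conclude that liver-related TEAEs were under-recorded, mainly on active treatment, so that the reported difference between arms is too small. The documents give no counts of enzyme rises, dosing stops or missing records by arm. They show neither that a case was lost nor the direction of any bias.

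This is an internal inconsistency of minor to moderate weight. It deserves attention because TEAEs are a primary endpoint in a study stopped for a liver signal.

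**What to change.** Reconcile the passages by stating in 8.5.2 that laboratory abnormalities meeting the 11.1.5 criteria are recorded as AEs regardless of the clinical-significance judgment. In the same pass, state whether the SAE sentence in 6.4 covers >=8 x ULN without signs of liver damage. Neither change alters a dosing rule.

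New wording cannot change what sites recorded during dosing: the Safety Monitoring Committee recommended termination on 26 November 2021 and the SAP is dated 17 December 2021. The useful step for this study is a listing-based check before database lock. Every IP interruption or discontinuation with a coincident qualifying laboratory value should have a linked AE, and sites are queried where none is found. If the database is already locked, report the reconciliation in the CSR.

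The cost is one protocol sentence or site memo, one query round and a few more AE records.

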8.5.3. Physical Examination

Physical examinations, including weight and height (at screening), will be conducted by a physician, trained physician’s assistant, or nurse practitioner as acceptable according to local regulation at visits specified in the Schedule of Activities in Section 8.11 (see also Section 8.1, “[Timing of Assessments](#)”). The person conducting the physical examination will document this in the subject’s medical source records. Clinically significant abnormal findings should be recorded as AEs.

Particular attention should go to physical examination at all visits, to identify any potential SARS-CoV-2 related signs and symptoms, indicating potential infection (e.g. cough, fever, headaches, fatigue, dyspnea, myalgia, anosmia, dysgeusia, anorexia, sore throat, etc). Subjects presenting such symptoms at screening/baseline should not be included/randomized in the study (see Section 6.2). Developing such symptoms during the study, should be managed as per Section 8.5.6.

8.5.4. Vital Signs

Vital signs (systolic and diastolic blood pressure, heart rate, and oral/tympanic body temperature, the same method of measuring body temperature to be used throughout the study) will be recorded in a standardized manner (i.e. after the subject has rested in a supine position for at least 5 minutes) at visits specified in the Schedule of Activities in Section 8.11 (see also Section 8.1, “[Timing of Assessments](#)”). Clinically significant abnormal values should be recorded as AEs.

8.5.5. 12-lead Electrocardiogram

At the time points specified in the Schedule of Activities (see Section 8.11 and also Section 8.1, “Timing of Assessments”), a 12-lead ECG will be recorded and results will be sent for central reading.

12-lead ECG recordings will be performed before blood sampling and after subjects rested for at least 5 minutes in supine position. In case an indwelling catheter is used, ECGs may be recorded after blood sampling, provided that there is at least 30 minutes between catheter insertion and the ECG recording. When catheter insertion would fail, the 12-lead ECG needs to be taken before the venipuncture and at least 30 minutes after the failed attempt. Triplicate ECGs (i.e. 3 ECGs) will be performed at Visit 1 (Day 1) predose and at 4.5 hours postdose, within a time span of 6 minutes, with an approximate 3-minute interval between ECGs. At all other timepoints, single ECGs will be taken.

The following parameters need to be recorded: heart rate, PR interval, RR interval, QRS interval, uncorrected QT interval, morphology, and rhythm analysis. QTcF will be derived. QTcF will be considered as normal if ≤ 450 ms, while a prolongation of QTcF to >500 ms and/or an increase from baseline >60 ms will be considered a threshold of concern.

Immediately after recording, the ECGs will be reviewed by the investigator to detect clinically significant abnormalities. This immediate review during the visit needs to be documented in the subject’s source. After receipt of the central report, also all flagged ECG abnormalities need to be assessed by the investigator on clinical relevance. Clinically significant abnormal findings should be recorded as AEs.

8.5.6. Other Safety Assessments

SARS-CoV-2 infection will be assessed at screening by RT-PCR and at baseline through careful physical examination to exclude any potential signs and symptoms of infection, e.g. cough, fever, headaches, fatigue, dyspnea, myalgia, anosmia, dysgeusia, anorexia, sore throat, etc.

Additional RT-PCR and serology testing will be repeated at baseline and throughout the study as needed. The repeat RT-PCR may be performed 2-3 days prior to the baseline visit to allow for results availability prior to randomization. The subject could be tested for SARS-CoV-2 in facilities outside the study site and if so, the subject should be instructed to immediately inform the study investigator if the test is positive and test results should be shared with the investigator as soon as possible.

8.6. Pharmacokinetic Assessments

[figure not shown]
Blood samples (2 mL) for the PK assessment should be collected on the visits specified in the Schedule of Activities in Section 8.11 (see also Section 8.1, “Timing of Assessments”). Samples will be obtained by venipuncture (or indwelling cannula), preferably in the forearm into tubes containing K2EDTA and will be immediately chilled (ice bath). Within 30 minutes after blood collection, the plasma will be separated in a refrigerated centrifuge at 4 °C for 10 minutes at circa 1500 g and transferred into tubes as described in the laboratory manual. The plasma samples will

be stored at approximately -60°C to -90°C at the site until shipment to the bioanalytical laboratory.

8.7. [REDACTED]

8.7.1. [REDACTED]

8.7.2. [REDACTED]

8.7.3. [REDACTED]

8.8. Other Assessments

8.8.1.

[REDACTED]

[REDACTED]

[REDACTED]

[REDACTED]

8.8.2.

[REDACTED]

[REDACTED]

[REDACTED]

8.8.3.

[REDACTED]

[REDACTED]

[REDACTED]

8.8.4.

[REDACTED]

[figure not shown]
[REDACTED]

8.8.5.

[REDACTED]

[REDACTED]

8.8.6. [REDACTED]

Subjects will be trained on how to complete the subject diary.

8.9. Sample Management

Total Blood Volume

The total amount of blood to be taken per subject over a period of 20 weeks for scheduled laboratory parameters will not exceed [REDACTED] mL. This includes sampling for safety, PK, [REDACTED] assessments.

Blood and Urine Samples for Routine Safety Tests, Serology, SARS-CoV-2, FSH, and Pregnancy Tests

All blood and urine samples for routine safety tests, serology, FSH, and pregnancy tests will be analyzed in a central laboratory and will be destroyed after analysis. SARS-CoV-2 tests may be analyzed in local laboratories and samples will be destroyed after analysis.

Blood Samples for PK [REDACTED]

After the end of the study (defined in Section 5.2), all biological samples obtained during the clinical study may be stored for a maximum period of 5 years, after which the samples will be destroyed. The sample storage period will be in accordance with the IRB/IEC-approved ICF and applicable regulations (e.g. Regulatory Authority requirements).

The stored samples shall only be used by the sponsor, sponsor partners, and/or other companies contracted by the sponsor, for research related to this clinical study. Any research outside the context described in this CSP may only be conducted after approval by the IRB/IEC and Regulatory Authority and after obtaining informed consent from the subject.

The details of blood and sample handling and shipment instructions for all samples collected during the study will be provided in a separate laboratory manual.

8.10.

8.11. Schedule of Activities

For detailed instructions on the clinical study procedures, please see referred sections and Section 8.1, “Timing of Assessments”.

EVENT	SCREENING PERIOD	TREATMENT PERIOD ¹						FOLLOW-UP PERIOD
		1	2	3	4	5	ED ²	
Study Visit	S	1	2	3	4	5	ED ²	Follow-up Visit
Study Week	-4 to -1	Baseline	1	4	8	12		
Study Day (D) ± Days	-28 to -1	1	8±1	29±2	57±2	85±2	Early treatment discontinuation	28 ± 3 after last IP dosing
Informed consent	✓							
Inclusion/exclusion criteria	✓	✓						
Demographics	✓							
Medical history	✓							
Physical examination	✓	✓	✓	✓	✓	✓	✓	✓
Vital signs	✓	✓	✓	✓	✓	✓	✓	✓
Body weight and height ³	✓	✓	✓	✓	✓	✓	✓	✓

¹ On dosing days, all assessments are to be performed predose, unless otherwise specified.

² Subjects who discontinue treatment early will be requested to return for an ED visit and to return for a FU visit 28 ± 3 days after last IP administration.

³ Height only to be measured at screening.

EVENT	SCREENING PERIOD	TREATMENT PERIOD ¹						FOLLOW-UP PERIOD
		1	2	3	4	5	ED ²	
Study Visit	S	1	2	3	4	5	ED ²	Follow-up Visit
Study Week	-4 to -1	Baseline	1	4	8	12		
Study Day (D) ± Days	-28 to -1	1	8±1	29±2	57±2	85±2	Early treatment discontinuation	28 ± 3 after last IP dosing
12-lead ECG ⁴	✓	Predose, 1.5h, 3h, 4.5h postdose ⁴	Predose	Predose	Predose	Predose	✓	✓
QuantiFERON-TB Gold test	✓							
SARS-CoV-2 RT-PCR test ^{5,6}	✓	✓	As needed					
SARS-CoV-2 serology test ^{5,6}		✓	As needed					
Randomization		✓						
Blood collection								
– Safety (hematology, coagulation, chemistry)	✓	✓ ⁷	✓	✓	✓ ⁷	✓ ⁷	✓	✓
– Safety (HBV, HCV, HIV serology)	✓							

⁴ At Visit 1 (Day 1), triplicate ECGs will be recorded predose and at 4.5 hours postdose. At all other timepoints, single ECGs will be taken.

⁵ RT-PCR from a nasal swab sample at screening and RT-PCR from a nasal swab sample and serology testing at Visit 1 (Day 1), and as needed when subject presents signs and symptoms of SARS-CoV-2 infection.

⁶ SARS-CoV-2 RT-PCR and serology tests can (optionally) be sampled by a nurse at the subject's home 2-3 days before Visit 1 (Day 1).

⁷ Fasted glucose, fasted insulin, and HOMA-IR only at Visit 1, 4, and 5.

EVENT	SCREENING PERIOD	TREATMENT PERIOD ¹						FOLLOW-UP PERIOD
		1	2	3	4	5	ED ²	
Study Visit	S							Follow-up Visit
Study Week	-4 to -1	Baseline	1	4	8	12		
Study Day (D) ± Days	-28 to -1	1	8±1	29±2	57±2	85±2	Early treatment discontinuation	28 ± 3 after last IP dosing
– Pregnancy test serum (all females)	✓							
– FSH test (WOnonCBP, non-surgical postmenopausal women)	✓							
– Blood samples for PK GLPG3970		Predose ⁸ , 0.5-1.5h, 2-2.5h, 4.5h ⁹ postdose ¹⁰	Predose ⁸	Predose ⁸	Predose ⁸ , 0.5-1.5h, 2-2.5h postdose ¹⁰	Predose ⁸	✓	
– [REDACTED]								
– [REDACTED]								
– [REDACTED]								

⁸ At Visit 1, 2, 3, 4, and 5, PK sample to be taken within 30 minutes predose.

⁹ At Visit 1, the PK sample collected at 4.5 hours postdose must be taken immediately after the triplicate ECG.

¹⁰ At Visit 1, 4, and 5 subjects must come for the study visits in a fasting state (no food intake for at least 8 hours). If the postdose samples could not be collected at Visit 4, they should be collected at Visit 5. It is important that the PK [REDACTED] samples are collected on the same day.

EVENT	SCREENING PERIOD	TREATMENT PERIOD ¹						FOLLOW-UP PERIOD
		1	2	3	4	5	ED ²	
Study Visit	S							
Study Week	-4 to -1	Baseline	1	4	8	12		
Study Day (D) ± Days	-28 to -1	1	8±1	29±2	57±2	85±2	Early treatment discontinuation	28 ± 3 after last IP dosing
Dispense IP		✓	✓	✓	✓			
IP administration ¹⁴		Once daily throughout the treatment period						
AE and concomitant medication	throughout the study							

13 [REDACTED]

¹⁴ At Visit 1 (Day 1), the IP will be administered at the study site in a fasted state. Breakfast will be provided to the subject 0.5-1 hour after the IP intake. Lunch should be eaten 1 hour before or after the ECG measurement at 4.5 hours postdose. At all other dosing days (including Visit 2, 3, 4, and 5), the IP should be taken in a fed state (together with a meal).

